Feeding in neonates involves a sequence of sucking, swallowing, and breathing that requires coordination of the face, head, and neck muscles with the myelinated vagal regulation of the bronchi and the heart (11). In preterm neonates, the muscles needed to feed are underdeveloped, resulting in the need for OT rehabilitation to 'learn' feeding patterns. Preterm neonates' inability to feed effectively is the primary reason for prolonged hospital stays (12). In neonates with HIE, development of cortex and basal ganglia is interrupted, and depending on the severity, normal developmental plasticity is hindered, further contributing to their inability to feed (13). Both types of feeding difficulties involve complex motor learning, which requires integration of sensory and motor pathways. Treating oromotor difficulties during the learned task of feeding with noninvasive brain stimulation that promotes plasticity, poses a highly novel application of taVNS. Our major premise is that in babies at high risk for motor problems, simultaneously delivered brain stimulation via taVNS will boost motor cortical plasticity involved in a learned feeding task, leading to better feeding.

This protocol has 2 specific aims that will be investigated:

Specific Aim 1: Improved Motor Learning - We aim to investigate whether pairing taVNS with rehabilitation training of feeding behavior in preterm and HIE neonates will enhance and accelerate the learning of effective feeding behavior in a dose responsive manner. We call this treatment "taVNS-paired feeding." The primary outcome measures of taVNS-paired feeding will be daily oral milk feeding volume changes from before to during treatment, and number of infants reaching full oral feeds

between once and twice daily taVNS-paired feeding, duration to full feeds, as well as general motor functional impairment as measured by [name] Test of Early infant motor Performance (STEP). Our hypothesis is that taVNS-paired feeding for preterm neonates is feasible, safe and effective at reducing length of stay solely for feeding reasons, compared to historical controls. As part of our safety investigations with separate funding, we may perform taVNS during a clinical modified barium swallow study with pediatric speech language pathologists performing the study and compare 10 swallows with stimulation on and off to determine if taVNS affects swallowing parameters.

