[name], Ph.D, obtained his doctorate under [name], and has extensive experience and background in clinical TMS and taVNS, especially in the development of novel protocols for neurological disorders. His thesis work involves systematic elucidation of the dose response of taVNS on heart rate, use of heart rate as a biomarker of taVNS effect, and the use of taVNS with fMRI in determining pathways and regions affected by taVNS in adults. He determined that the 'on' pulse heart rate change was a mean of -3 beats per minute (bpm) while the 'off' pulse heart rate change was +6 bpm. Although these are statistically significant and measurable changes, they are physiologically insignificant. Nevertheless, this will be an important biomarker for infants, but is not expected to result in safety concerns. [name] careful and thorough studies lay the safety and efficacy groundwork for the current proposal.

D. RESEARCH DESIGN AND METHODS (including data analysis)

Due to the novelty of these studies, [name] will be present for each taVNS-paired feeding session conducted in the first participants, and as needed thereafter. [name] and or [name] will monitor taVNS effects. If any adverse events are noticed which are not described in the consent or are serious, we will inform the IRB before continuing with the next enrolled subject. Importantly, all of these methods have been done before, and published by our and other groups in adults, and we believe these extra precautions will assure the safety and well-being of any participants enrolled.

taVNS-paired feeding to enhance feeding behavior in neonates

Screening

Prospective participants will be identified by the PI ([name]) at the MUSC neonatal intensive care units (Level II and III), and checked for potential inclusion (please see the uploaded taVNS screening form). [name], and other clinical OTs based in the nursery may also mention the study to parents and refer them to [name] if they are interested in participating.

Participants

Inclusion criteria:

Infants must be clinically stable, on minimal respiratory support (nasal cannula, or room air), in discussions about Gtube placement for poor po feeding and are currently greater than or equal to 39 weeks post-menstrual age and

- 1) If born premature have been working on oral feeding for 30days;
or

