- 2) If term Infant with significant medical issues that have precluded oral feeding, such as hypoxic ischemic encephalopathy (HIE), have been working on oral feeding for 14days.

Exclusion criteria:

- 1) Unstable infants or those requiring respiratory support involving positive pressure.
- 2) Major unrepaired congenital anomalies
- 3) Anomalies/conditions that limit feeding volumes
- 4) Cardiomyopathy
- 5) Repeated episodes of autonomic instability (apnea or bradycardia) which are not self-resolving *

*Preterm infants commonly have short periods of shallow or absent breathing or lower heart rate termed apnea and bradycardia, respectively, and most are being treated for these physiologic manifestations of prematurity with caffeine, an effective central stimulant. Infants are on cardiorespiratory monitors through the nursery stay to capture events, many of which are self-resolving. Infants who require repeated episodes of tactile stimulation to come out of these events are defined as *unstable*.

Neonates who are beginning oral feeds after medical treatment for critical illnesses, such as HIE brain injury, will be included as these neonates represent a population in which taVNS-paired feeding could present the largest success in overcoming impaired brain development. Congenital syndromes may be included if the infants do not have major, unrepaired anomalies or anomalies that limit feeding volumes.

Written informed consent will be obtained from the mother if available and if she has custody or decision making authority for the participant, otherwise a parent or legal guardian, prior to participation in the experimental paradigm. Department of Social services may have custody of infant but require the parent or foster parent to consent for all medical procedures.

Electronic Consent will be used for situations when the parent (or Legally Authorized Representative) is at another hospital and cannot travel to MUSC to provide consent in person. We will use the approved REDcap system to obtain consent. [name] or other approved study personnel will go over the entire consent document on the phone with the parent to ensure comprehension and to confirm identity. Parent will be given a copy of the completed, signed consent form in person or by email or fax.

Study Design

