Up to 40 preterm/HIE neonates will be enrolled in this prospective, open-label safety and feasibility trial, with a dose response. The experimental paradigm consists of 2 to 3 weeks of once or twice daily taVNS-paired feeding.

Our control group was investigated by Drs. [name] and [name] at MUSC, who have researched all infants failing feeding and getting Gastrostomy tubes in our nurseries over the past 5 years. We can compare our data to this historical group at our own institution.

All consented participants will receive the active stimulation condition.

taVNS Stimulation (in Detail)

After obtaining consent and describing this procedure to the parents and all members of the baby's care team, we will first, with a 500 μ s, 25Hz pulse, gradually increase the intensity of the TENS unit until the baby can first feel something in their ear. We will use the facial expression change and fidgety movements to determine when the infants feel the stimulation. This intensity will be recorded as the perceptual sensory threshold. The stimulation intensity we will use for this study on taVNS-paired feeding is a small decrement from the perceptual sensory threshold for each infant (-0.1mA), a point at which they should not react to the stimulation. We will retest the sensory threshold before every session.

Determination of Perceptual Threshold

1. Electrode clip will be placed on the left tragus in an enrolled infant at rest. Starting at 0.2mA at 25Hz, we will deliver 5 seconds of pulses, and increase by 0.1mA until the perceptual threshold is achieved by observation of the infant's facial expression, fidgety movements, or NIPPS score. This will be termed the perceptual threshold.
2. We will then deliver this level of microcurrent while the infant is feeding on the first day to determine if the perceptual threshold changes with feeding. Current will then be held constant while pulse width and frequency will be set at 500us and 25Hz, respectively.

3. Finally, we will decrease the microcurrent by 0.1mA *below the perceptual threshold* and administer this taVNS treatment during the feeding and deliver this only while the infant is actively sucking from the bottle.
4. The total duration of this 'on-and-off' taVNS stimulation treatment will continue for 30 minutes or the duration of the feed.
5. We may manually trigger the taVNS stimulation or place a gel EMG electrode over the temporomandibular joint area to trigger the taVNS impulse.

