Once the daily taVNS intensity has been determined, the treatment will continue to be administered in conjunction with the daily OT feeding once or twice daily.

As the baby begins to suck from the bottle or breast, stimulation will be triggered and a timer will be started. Sometimes the infant has non-nutritive sucking and it is difficult for the operator to discern between these lip motions and real suck/swallow. We wish to stimulate during sucking motions that include swallowing but may occasionally pair with ineffective and incomplete lip sucking, characteristic of more immature patterns. We may use manual triggering by a research assistant or triggering by the EMG at the buccinator muscle to ensure accurate delivery of impulses and pairing of impulse with sucking/swallowing.

The stimulation will continue until the baby stops sucking, at which point the stimulation will be stopped and the timer will stop, until the baby begins to suck again. The typical feeding OT session lasts up to 30 minutes. Physiological data will be monitored continuously as measured by the echocardiogram (ECG). Neonatal Infant Pain Scale (NIPS) data will be collected at beginning, middle and the end of treatment session. The NIPS rating scale currently in use in the nursery is included in this submission. These studies will be conducted in both level II and III Neonatal Intensive Care Units (NICUs), depending on the location and of the enrolled participants.

taVNS Device

taVNS will be delivered to the left ear only using an active (tragus) location for the taVNS clip using either the Digitimer Type DS7AH (Digitimer Ltd, Hertfordshire, England) or Soterix 0125-LTE stimulator customized for our infant trials. Both are TENS units and are cleared by the FDA for electrical nerve stimulation in research trials (See uploaded documents from Soterix). We also recently received FDA Breakthrough device designation for our BabySTrong taVNS infant feeding system, based on a customized 0125-LTE Soterix taVNS unit. TENS units are widely used in children with overactive bladder and dysfunctional voiding and stooling (44-45) and for analgesia in children, and as a treatment for chronic pain, including cancer (46). A custom electrode, embedded within a carbon matrix will be used to stimulate the auricular branch of the vagal nerve at the tragus. We will then trigger the taVNS unit to deliver the microcurrent or to stop the microcurrent when the infant is actively sucking and swallowing.

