For safety we will compare HR changes from baseline to during taVNS within subjects. We will compare treatment before and after the taVNS-paired feeding treatment for the rate of feeding volume increase, and days to full po feeds. We will use repeated measures ANOVA to analyze repeated measures such as HR over 5 minutes and mean daily feeding volumes in 7-10 day epochs. We will analyze the number of infants who reach full feeds vs requiring G-tube during taVNS-paired feeding, between once and twice daily stimulation by Chi-squared. We will assess differences in kurtosis parameters from pre-to post taVNS scans by paired t-test, and between those that reach full oral feeds vs those that require a Gtube by unpaired t-test.

Estimated Difficulties, Limitations and Time Frames

Estimated Difficulties. Many of the initial parameters for taVNS in humans, such as frequency and pulse width, were accomplished in trials at MUSC by [name] et al. that were approved by the IRB. In one sense, we will be shrinking many of the components into miniature form to deliver stimulation to neonates and infants. In spite of the clear differences in size and skin between the neonatal and adult ear, the custom electrodes have been fitted to several different weights of infants (2.5-4.0 kg).

Limitations. We will not be delivering a SHAM stimulation paradigm (electrodes and Digitizer with appearance of taVNs treatment without actual current). Our goal is to determine safety and feasibility of active treatment with a dose response in order to investigate whether this should be administered in a larger randomized control trial. In this respect, the comparison we lose in not having a SHAM stimulation is offset by the validation we will receive in the safety and feasibility of active treatment. We will compare our overall results with characteristics of infants who required a Gtube from [name] and [name]'s publications.

Estimated Time Frames. The duration of the study will likely be ~4 years, with 2 years of active enrollment and 18 months of follow-up.

E. PROTECTION OF HUMAN SUBJECTS

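### The plan compares once with twice daily taVNS on reaching full feeds but gives no rule for assigning frequency, so the unadjusted chi-squared cannot support a feeding dose response

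*Combined protocol and SAP*

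**What the plan says.** Specific Aim 1 says that pairing taVNS with feeding training should improve "the learning of effective feeding behavior in a dose responsive manner". Its primary-outcome sentence, which runs across a page break, covers the change in daily oral volume and the number of infants reaching full oral feeds "between once and twice daily taVNS-paired feeding, duration to full feeds". Under Study Design the trial is a "prospective, open-label safety and feasibility trial, with a dose response" of up to 40 infants. The Limitations paragraph repeats the dose response as part of the goal that informs a larger randomised trial.

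On frequency itself, Study Design says "The experimental paradigm consists of 2 to 3 weeks of once or twice daily taVNS-paired feeding", and the stimulation section says treatment is given "in conjunction with the daily OT feeding once or twice daily". All infants receive active stimulation, which says nothing about frequency.

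Enrolment pools two groups with different entry rules. For the first, the rule is "If born premature have been working on oral feeding for 30days". The second is term infants with significant medical problems such as HIE, who "have been working on oral feeding for 14days".

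The Data Analysis section compares "the number of infants who reach full feeds vs requiring G-tube during taVNS-paired feeding, between once and twice daily stimulation by Chi-squared". It names no stratum or covariate.

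**The concern.** A dose-response contrast needs a known route by which each infant received its dose. Here frequency could follow infant type, severity, tolerance, staff or family availability, or calendar period. A 2x2 chi-squared attributes any difference to frequency, whatever the route. If prognosis and frequency are linked, the result can show a dose effect that is not there or hide one that is.

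The endpoint adds a second difficulty. Outcomes are counted during a course that may last two weeks or three, with no common time. An infant who is at neither full feeds nor G-tube when the course ends has no stated cell in the table, and full oral feeds has no operational definition. If course length differs by frequency, so does the opportunity to succeed.

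What is at stake is the feeding dose-response reading in Aim 1 and that part of the stated basis for a later trial.

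**Working it through.** **Is there a rule?** Study Design, the stimulation section, Data Analysis and Limitations state no randomisation, alternation, sequential cohorts, clinical criterion, allocation ratio or number per frequency. The only randomisation mentioned for this treatment belongs to a possible later trial. Limitations discusses the missing sham but not how frequency is assigned. Part of section C (Preliminary Studies) was not in the text available. A rule there is unlikely but cannot be excluded.

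**Is there a figure to reproduce?** No. The plan gives no alpha, power, full-feed rate or split by frequency. What follows is illustration.

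**Assumptions (not in the documents).** 20 infants per frequency, 20 of each infant type, two-sided 5% level, no true frequency effect, no dropout. The type with the better prognosis has full-feed rate p1 and the other p2. One frequency group holds a infants of the better type and the other holds b, with a + b = 20.

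**Spurious difference.** Each crude rate is a weighted average of p1 and p2, so the expected difference is (p1 − p2)(a − b)/20. For p1 = 0.70, p2 = 0.40 and a 14/6 versus 6/14 mix, this is 0.30 × 8/20 = 0.12.

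**False-positive rate.** The number of successes in each group is the sum of two binomials. Adding the probabilities of all tables with chi-squared above 3.84 gives the following rates (uncorrected / continuity-corrected):

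| Rates by type | Balanced 10/10 | 12/8 vs 8/12 | 14/6 vs 6/14 | 16/4 vs 4/16 |
|---|---|---|---|---|
| 60% vs 50% | 4.3 / 1.7% | 4.5 / 1.8% | 5.0 / 2.1% | 5.9 / 2.6% |
| 60% vs 40% | 3.8 / 1.5% | 4.5 / 1.9% | 6.5 / 3.0% | 10.0 / 5.0% |
| 70% vs 40% | 3.4 / 1.3% | 4.9 / 2.0% | 9.6 / 4.6% | 18.2 / 10.0% |

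For the last two columns the spurious differences are 4 and 6 points, 8 and 12 points, and 12 and 18 points, row by row.

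**Could such mixes arise by chance?** If assignment is unrelated to type, a is hypergeometric (40 infants, 20 of the better type, 20 drawn). P(a ≥ 14 or a ≤ 6) = 2.6%, and P(a ≥ 16 or a ≤ 4) = 0.04%. The right-hand columns therefore need assignment that is linked to type.

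**Uneven types.** With 32 preterm and 8 term/HIE infants (also assumed) and all 8 in one frequency group, the uncorrected rate is 7.0% at 60% vs 40% and 12.0% at 70% vs 40%, taking preterm as the better type.

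**What stratifying does.** In all 12 table scenarios the Mantel-Haenszel risk difference averages 0, and the Cochran-Mantel-Haenszel (CMH) test without correction rejects 4.3% to 5.2% of the time. Each stratum has weight n1·n2/(n1 + n2), so a stratum with only one frequency has weight 0. In the 32/8 example the 8 term/HIE infants drop out of the comparison.

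**Precision.** At 20 per group and a rate near 50%, the 95% half-width is 1.96 × √(2 × 0.25/20) = 0.310, or about 31 points.

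**The case against.** The protocol limits its own claims. Background puts the improvement hypotheses second to safety and feasibility. The section on potential benefits says that avoidance of a G-tube cannot be determined from this study, and a definitive answer is left to a later randomised trial. At an assumed 20 per group, power for 50% vs 70% is only about 25%, so the test supports little even when unbiased. All this limits the stakes. It does not supply the missing rule, because Aim 1 still lists the contrast among the primary outcomes and claims a dose response.

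Infant type is also not a demonstrated confounder. Both groups must be stable, not progressing with OT and in discussion of a G-tube, so their prognoses may be close. Stratifying by type would leave every other determinant of frequency untouched. This stands, and it is why adjustment alone is not an adequate answer.

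A reader might infer that frequency in fact follows infant type and that the test is therefore inflated. No section shows such a link, and the table shows near-nominal error when the gap or the imbalance is small. A reader might also infer that all dose-response wording should go. In Study Design and Limitations that wording also covers safety and feasibility, and describing tolerability by frequency remains legitimate in a non-randomised pilot.

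**Conclusion.** The concern holds in a limited form and should be fixed. With no stated assignment rule, and no statement that frequency is fixed within an infant, the crude contrast cannot separate a frequency effect from whatever determined the frequency. It therefore cannot support the feeding dose-response claim in Aim 1, or the same part of the goal in Limitations.

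This conclusion rests on the text alone. The size of any bias does not: the 4- to 18-point spurious differences and the 5.0% to 18.2% uncorrected error rates (14/6 and 16/4 mixes) depend on assumed rates, an assumed 20:20 split and assumed imbalance. Inflation is material only when the prognostic gap is large and assignment is strongly linked to type, and the documents establish neither. The safety and feasibility aims are not undermined.

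**What to change.** 1. **Assignment (main change).** Where both frequencies are open to each infant at enrolment, allocate them 1:1 at random, stratified by preterm versus term/HIE, and analyse by allocated frequency even if it later changes. The cost is a list, a short amendment and less freedom in scheduling sessions. If this is not possible, state the assignment rule and show baseline characteristics by frequency. The birth history and medical conditions listed under Sources of Materials are already collected. Label the feeding comparison as descriptive and not evidence of a dose response. Safety and tolerability may still be described by frequency.

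2. **Analysis.** In either case, replace the crude chi-squared with a comparison stratified by infant type, for example CMH or a Mantel-Haenszel risk difference with a score interval. Say that this removes bias from infant type only and that a stratum with only one frequency contributes nothing.

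3. **Endpoint.** Define full oral feeds operationally. Count every infant as reaching or not reaching it by one common time after first stimulation, the same for both frequencies. Infants at neither full feeds nor G-tube count as not reaching. If that time falls after a shorter course ends, say that the endpoint includes time off treatment.

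Items 2 and 3 cost text only, and nothing here needs extra infants. None of it makes the contrast precise. This takes no position on which frequency or course length is clinically right.

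### Once and twice daily stimulation are compared only on full feeds yes or no; the volume and time outcomes that measure speed of learning have no stated dose comparison

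*Combined protocol and SAP*

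**What the plan says.** The Combined protocol and SAP makes dose part of both the aim and the design.

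- **Aim (section A, Specific Aim 1).** The question is whether paired stimulation will "enhance and accelerate the learning of effective feeding behavior in a dose responsive manner".
- **Outcomes (same place).** The primary measures are "daily oral milk feeding volume changes from before to during treatment, and number of infants reaching full oral feeds". The text then breaks and continues "between once and twice daily taVNS-paired feeding, duration to full feeds".
- **Design (section D, Study Design).** "Up to 40 preterm/HIE neonates will be enrolled in this prospective, open-label safety and feasibility trial, with a dose response". Treatment lasts 2 to 3 weeks, given once or twice daily. Neither the number of infants per frequency nor the way frequency is assigned is stated.
- **Analysis (section D, Data Analysis).** Volumes are covered by this sentence: "We will use repeated measures ANOVA to analyze repeated measures such as HR over 5 minutes and mean daily feeding volumes in 7-10 day epochs". A before-and-after treatment comparison is planned "for the rate of feeding volume increase, and days to full po feeds". Full feeds versus G-tube is compared "between once and twice daily stimulation by Chi-squared". That is the only analysis that names the two frequencies.

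**The concern.** To accelerate is to change speed, and the one outcome compared between frequencies carries no information on speed. An infant who reaches full feeds on day 4 counts the same as one who gets there on day 18. The outcomes that do measure speed (daily volume, its rate of increase, days to full feeds) are analysed over time or before against after treatment, with no stated contrast between once and twice daily.

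Section D, Limitations, says the trial is meant to inform a larger randomised trial. A non-significant chi-squared in at most 40 infants could be carried forward as absence of a dose response, while volumes recorded every day go unused for that question.

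**Working it through.** **Inputs.** From the documents: up to 40 infants, two frequencies, 2 to 3 weeks of treatment. Not in the documents, so assumed: two-sided 5% level; 20 infants per frequency (range 30/10 to 10/30); full-feed rates as shown; a normal underlying feeding scale on which full feeds is a cut-point. The plan states no power or effect size, so there is no figure to reproduce.

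**Step 1. Power of the planned test.** The shift on the normal scale is d = z(p2) − z(p1); for 50% vs 80%, d = 0.842 − 0 = 0.842. Chi-squared power comes from exact enumeration of two binomials, without continuity correction. The t-test uses the noncentral t with 38 df and noncentrality d × √(20/2); for d = 0.842 that is 2.66. The last column caps each infant's value at the full-feeds threshold (simulation, 40,000 runs).

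| Full feeds, once vs twice daily | d | Chi-squared | t-test, uncapped | t-test, capped |
|---|---|---|---|---|
| 50% vs 70% | 0.524 | 25% | 37% | 25% |
| 50% vs 75% | 0.674 | 37% | 55% | 36% |
| 50% vs 80% | 0.842 | 53% | 74% | 50% |

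A continuity correction lowers the chi-squared to 14% in the first row and 37% in the last. For 50% vs 80% with 30 infants on once daily and 10 on twice daily, the figures are 40% (chi-squared) and 61% (uncapped t-test); with 10 and 30, the chi-squared has 46%. By the normal approximation at 20/20, the chi-squared reaches 80% power only for gaps such as 30% vs 73%, 40% vs 82% or 50% vs 90%.

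**Step 2. Share of information kept by a yes/no cut.** Against an unadjusted, uncapped normal outcome the share is φ(c)² / [p(1 − p)], with c the cut-point.

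- p = 50%: 0.399² / 0.25 = 0.64
- p = 40%: 0.62
- p = 30%: 0.58
- p = 20%: 0.49

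The loss is therefore about 36% to 42% for rates of 30% to 50%. Against a volume analysis adjusted for a baseline with correlation ρ, multiply by (1 − ρ²). At p = 50%:

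- ρ = 0.5: 0.637 × 0.75 = 0.48
- ρ = 0.7: 0.637 × 0.51 = 0.32 to 0.33
- ρ = 0.8: 0.637 × 0.36 = 0.23

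The loss passes one half at ρ of about 0.46 when p = 50%, or without adjustment when p is about 20% or lower.

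**Step 3. Which volume summary.** Volume cannot keep rising once full feeds are reached, so a fitted straight line misleads. Take two infants with the same starting gap to full volume (set to 1), each rising linearly to full feeds, on day 4 and on day 18, then flat to day 21. Over days 0 to 21 the least-squares denominator is 22 × (22² − 1)/12 = 885.5.

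- Day 4 infant: slope = (10.5×1 + 9.5×0.75 + 8.5×0.5 + 7.5×0.25)/885.5 = 23.75/885.5 = 0.027 per day. Mean shortfall = 2.5/22 = 0.11.
- Day 18 infant: slope = (826.5/18)/885.5 = 45.9/885.5 = 0.052 per day. Mean shortfall = 9.5/22 = 0.43.

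The faster learner gets about half the slope, while mean volume ranks the two correctly. A simulation with volumes capped at full feeds (20 per group, one set of assumed trajectories) points the same way. Power was 26% for a linear daily slope, 47% for the chi-squared, 56% for time to full feeds and 64% for baseline-adjusted mean treatment-period volume. The order matters here; the values depend on the trajectories assumed.

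**The case against.** **Silence is not exclusion.** The ANOVA sentence names a method and some repeated measures but lists no model factors, and the outcome sentence in Specific Aim 1 is broken and loosely punctuated. A frequency factor may have been intended for volume or for duration to full feeds. This stands in part: a reader might infer that the plan rules out a dose comparison of volume, and it does not. But no such comparison is stated, and the fix is the same under either reading.

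**The gain depends on assumptions.** This stands. A reader might infer that most of the dose information is lost. The documents give no SD, correlation or full-feed rate, and at rates of 30% to 50% an unadjusted comparison loses less than half. If full feeds is a ceiling on volume, a single unadjusted volume does no better than the chi-squared (50% against 53%). The gain has to come from the course before the ceiling and from baseline adjustment.

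**A slope is the obvious measure of acceleration.** It is a tempting choice of main estimate, but the plateau distorts it (step 3).

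**This is a pilot.** The trial is an open-label safety and feasibility study, and the close of section B ranks the efficacy hypotheses below safety and feasibility. This also stands: the trial need not be powered for dose. It argues for estimates with intervals, and does not justify leaving the speed outcomes out of a dose question the plan itself poses.

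**Confounding.** Assignment to frequency is not described, so a frequency term cannot make the comparison unconfounded. True, and it applies equally to the planned chi-squared.

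**Conclusion.** The concern holds in this form: the aim asks about dose-related speed of learning, and the only stated dose comparison is a yes/no count that ignores speed. A substantial part of the dose information already being collected goes unused. How large a part cannot be fixed from the documents. On an uncapped normal scale the loss is about 36% to 42% at full-feed rates of 30% to 50%, rising to about 77% against a volume analysis with baseline correlation 0.8. With a ceiling at full feeds and a single unadjusted volume, the advantage disappears. All of these figures treat full feeds as a cut on the same scale as volume and assume a two-sided 5% level; the power figures also assume a split of the 40 infants.

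The change should be made, but it is not critical to a feasibility trial. A reader should not infer that a frequency term would give an adequately powered or causal dose comparison: the sample is small and the route to once or twice daily is unstated.

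**What to change.** In section D, Data Analysis:

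1. Add frequency (once or twice daily) and frequency by epoch to the repeated-measures volume model, adjusted for pre-treatment volume. Report the baseline-adjusted difference in treatment-period volume, with its 95% CI, as the main dose estimate. Fix one common window, since courses run 2 to 3 weeks and epochs 7 to 10 days, and say how days after early discharge or G-tube placement are handled.
2. Compare time to full oral feeds by frequency, counting G-tube infants as not reaching full feeds.
3. Keep the full-feeds count as supportive, shown as a difference in proportions with 95% CI.
4. Do not make a linear daily slope the main estimate.
5. State how infants come to receive once or twice daily treatment, and label the dose estimates exploratory and possibly confounded.

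The cost is a few sentences in the plan and slightly more analysis, with no new data.
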